The Official Title

A Randomized Controlled Study of Lenvatinib Following Liver Transplantation in
Patients with High-Risk Hepatocellular Carcinoma

NCT number: none

Date of the document: November 16, 2019

Hepatocellular carcinoma (HCC) is the third leading cause of cancer deaths worldwide and accounts for about 13,000 deaths in the United States per year [1]. Liver transplantation offers selected patients with localized HCC a chance for cure. For those meeting the Milan criteria, defined as a single tumor 2–5 cm or three or fewer nodules, each 3 cm or less, and no gross vascular invasion, 5 year survival for transplanted patients is about 75% [2, 3]. Meeting these criteria provides additional priority for transplantation in the US. However, for those with HCC beyond the Milan criteria, whether determined pre-transplant or by pathologic evaluation of the explant, the risk of recurrence may be as high as 70% at 2 years after transplantation [4]. There are few studies evaluating adjuvant therapy after resection or transplantation for HCC, and there is no standard of care for the treatment of these patients. Finding an effective agent which decreases recurrence rates in high-risk patients would be a significant advance.

1. Research Purpose

The aim of this study is to observe the efficacy and safety of lenvatinib in preventing high-risk recurrence of hepatocellular carcinoma patients after liver transplantation.

2. Research Protocol

The research is an open, randomized, single-center study. Patients with high-risk recurrence of hepatocellular carcinoma who underwent liver transplantation are included according to the criteria of admission. After operation, the regimen of calcineurin inhibitors, mycophenolate mofetil, sirolimus or everolimus with glucocorticoids removed at an early stage are used. Patients enrolled in the study were randomly allocated in the lenvatinib group (54 patients) and the control group (54 patients) after stable condition. Patients in the control group are given supportive treatment and regular follow-up. Patients in the lenvatinib group are given lenvatinib within 1-2 months after operation (dose: body weight < 60 kg: 8 mg/day, body weight \geq 60 kg 12 mg/day). The baseline data of patients are collected before allocation. Serum and imaging examination are checked regularly every month to monitor the

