3.3 Exclusion criteria

- Life expectancy is less than 3 months
- The recurrence and metastasis of hepatocellular carcinoma are highly suspected.
- Patients are with other malignant tumors simultaneously. λ Patients are anaphylaxis to the inactive ingredients of lenvatinib or drugs.
- Pregnant or lactating women (Female participants need pregnancy test within 7 days before treatment).
- Preoperative history of severe cardiovascular disease: congestive heart failure $>$ NYHA grade 2; active coronary heart disease (myocardial infarction occurred within 6 months before entry into the study); severe arrhythmia requiring antiarrhythmic treatment (allowable use of beta-blockers or digoxin); uncontrolled hypertension.
- History of HIV infection.
- Severe clinical active infections ($>$ NCI-CTCAE version 3.0).
- Epilepsy patients requires medication (e.g. steroids or antiepileptic drugs).
- Patients with kidney diseases requires renal dialysis.
- Drug abuse, medical symptoms, mental illness or social status that may interfere with participants' participation in research or evaluation of research results.
- Patients who could not swallow oral drugs, such as those with severe upper gastrointestinal obstruction and need gastric tube feeding.
- Other anti-angiogenesis therapies, surgery, TACE, local therapy and systemic

chemotherapy were given before the treatment after liver transplantation.

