4.4 Follow up

- Once the treatment is initiated, patients will be regularly monitored for blood and imaging examination. Blood test includes alpha-fetoprotein, alpha-fetoprotein variants, abnormal prothrombin once a month. Imaging examination includes liver ultrasonography once a month, liver MR or CT scanning every 3 months, lung CT every 3 months.
- Multidisciplinary teams determine whether tumors recur based on imaging and serological examinations.
- The follow up duration time is 5 years.
- The primary endpoint is tumor recurrence which refers to the time from treatment to tumor recurrence. Overall survival refers to the time from treatment to death for any reason. The 1, 3, 5-year recurrence-free survival rate and the 1, 3, 5-year overall survival rate will be analyzed.
- The side effects during treatment were recorded. At the same time, patients' status will be scored according to ECOG PS score. Acute or subacute toxicity is classified as level of 0-4, 0 as non-response, 1 as mild, 2 as moderate, 3 as

severe and 4 as life-threatening. The severity of adverse events was judged, reported and handled according to GCP requirements of clinical trials.

5. Safety

Lenvatinib is a clinically approved drug. This study will be conducted in strict accordance with drug specifications and doses.

6. Data analysis and statistical methods

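### The 0–4 toxicity scale has no level for a fatal adverse event, and deaths are counted without cause, so the safety results cannot identify fatal adverse events

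*Combined protocol and SAP*

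**What the plan says.** Section 1 makes safety part of the purpose: "The aim of this study is to observe the efficacy and safety of lenvatinib in preventing high-risk recurrence".

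Section 4.4 sets out how safety is measured. The recording window is given by "The side effects during treatment were recorded". The scale begins "Acute or subacute toxicity is classified as level of 0-4, 0 as non-response, 1 as mild, 2 as moderate, 3 as", and the words that complete its top two levels are "severe and 4 as life-threatening". A further sentence adds: "The severity of adverse events was judged, reported and handled according to GCP requirements of clinical trials". The same section sets the length of follow-up: "The follow up duration time is 5 years".

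Death appears in two other places. Section 4.4 defines an endpoint that counts it: "Overall survival refers to the time from treatment to death for any reason". Section 3.4 lists it among the conditions for leaving the study and asks for an evaluation, which covers adverse events, within 1–2 weeks of the last medication.

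A named grading system appears once, in an exclusion criterion in section 3.3: "Severe clinical active infections ($>$ NCI-CTCAE version 3.0". Section 6.2 describes Kaplan–Meier curves and Cox models and gives no safety summary.

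**The concern.** The stated scale ends at life-threatening. An investigator with a fatal adverse event to grade can enter it at level 4, together with events the patient survived, or leave it without a grade. The text does not say which.

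The wording also ties the scale to acute or subacute toxicity, and neither term is defined. Nothing says how toxicity of slower onset or longer persistence is graded. Recording runs during treatment, but the protocol states no treatment duration. The control group receives no study drug, so it is unclear when its window opens and closes.

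At stake is the benefit–risk judgement. Lenvatinib is given here to prevent recurrence after an operation that the introduction describes as offering a chance of cure. In that setting a very small number of treatment-related deaths could decide the conclusion.

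**Working it through.** The plan states no figure on this point, so the check is mainly a reading of the text.

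**1. Where a fatal adverse event could show up**

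| Place | What it captures | What it does not give |
|---|---|---|
| 4.4, toxicity scale | Severity 0 to 4 | A level for death |
| 4.4, severity judged under GCP | Adverse events generally, with no acute/subacute limit | A named scale, a fatal category, a time window |
| 4.4, overall survival | Every death | Cause or relatedness |
| 3.4, exit conditions | The fact of death; an adverse event evaluation near the last medication | Grade, cause or relatedness of the death |
| 6.2, statistical methods | Efficacy and prognostic analyses | Any safety table by grade |

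Death itself is captured. No row yields a count of fatal adverse events.

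**2. What the scale merges.** Compare two possible results in one arm, with fatal events entered at level 4:

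- Result A: 2 fatal events and 0 survived life-threatening events, so level 4 = 2 + 0 = 2.
- Result B: 0 fatal events and 2 survived life-threatening events, so level 4 = 0 + 2 = 2.

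The tables are identical. If fatal events are left ungraded instead, result A shows 0 at level 4.

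**3. The numbers likely to be involved.** Section 2 gives 54 lenvatinib patients. One event is 1/54 = 1.9%, and two are 2/54 = 3.7%. The documents give no fatal-event risk, so the following rests on an assumed range. The expected count is 54 × p, and the chance of at least one event is 1 − (1 − p)^54.

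| Assumed risk p | Expected count | Chance of at least one |
|---|---|---|
| 1% | 0.54 | 0.42 |
| 2% | 1.08 | 0.66 |
| 5% | 2.70 | 0.94 |

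Across this range fewer than three fatal events are expected, so each needs to be identifiable.

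**4. Whether overall survival would reveal them.** Section 6.1 assumes a median recurrence time of 24 months on lenvatinib. With all 54 patients followed that far, about 54 × 0.5 = 27 would have recurred. Recurrences are not deaths, and the documents give no death rate after recurrence. Even so, one or two drug-related deaths could easily be lost among cancer deaths when cause is not recorded. Section 2 also lets control patients add lenvatinib at recurrence, so the all-cause comparison between arms is not a clean measure of drug harm.

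**5. Late toxicity.** The firmer limit is the recording window. It has no stated length for the lenvatinib group and no clear meaning for the control group, against 5 years of follow-up. The words acute or subacute add a second, undefined limit on what is graded.

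**The case against.** The strongest reply is that the trial does not miss deaths. Overall survival counts every death, at 1, 3 and 5 years, and the arms are randomised, so a sizeable excess on lenvatinib would show there. Section 3.4 adds an adverse event evaluation at exit, and section 4.4 has a separate sentence placing severity under GCP. This stands as far as detection goes. It does not supply attribution, because none of these places asks for cause or relatedness and the GCP sentence names no scale.

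A reader might infer several stronger things that the documents do not support:

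- **That harm is understated.** Entering a fatal event at level 4 coarsens the table without lowering the level-4 count, and deaths are counted elsewhere. No direction of bias follows.
- **That the 0–4 scale is the trial's only safety instrument.** The GCP sentence and the exit evaluation exist. The part of section 7 before 7.2 was not available for review, and nothing is inferred from that.
- **That a calculable share of follow-up goes ungraded.** The plan defines no cut-off for acute or subacute. The relevant denominator would be the treatment period, which is not stated, and not the 5 years. A toxicity that begins late in treatment can still be acute in onset.
- **That infection is graded one way at entry and another as an outcome.** Section 3.3 uses NCI-CTCAE only to exclude patients, and no text makes infection a graded outcome. An entry threshold and an outcome scale may differ without contradiction.

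**Conclusion.** The point holds as a gap in classification and attribution. The scale in 4.4 has no fatal level, and deaths are recorded without cause or relatedness. The safety results therefore cannot separate fatal adverse events from survived life-threatening events or from cancer deaths. Grading of toxicity that is not acute or subacute, and the length of the recording window, are unspecified.

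The gap applies to any fatal adverse event that occurs. How many will occur, and the size and direction of any bias, cannot be derived. The percentages and expected counts above only illustrate scale: they use the planned 54 patients and assumed risks of 1% to 5%. The conclusion needs no assumption beyond the wording of 3.4, 4.4 and 6.2. The plan should be changed, but the point does not threaten the primary comparison.

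**What to change.** Amend section 4.4 and add a short safety paragraph to 6.2:

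- Grade all adverse events in both groups with one stated version of NCI-CTCAE, which section 3.3 already names, including a fatal category. Remove the restriction to acute or subacute toxicity.
- State one recording window that applies to both arms, with a start and an end that do not depend on taking study drug (for example, starting at randomisation).
- Record relatedness or cause for every death. The trial is open, so show fatal events by arm regardless of relatedness as well as by relatedness.
- Tabulate worst grade per patient by arm, with fatal events on their own line.

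This changes measurement and reporting only. It takes about a paragraph of amendment and a change to the case report form, with no added tests or visits, since 4.4 already has monthly checks. The downside is slightly more form work and a safety table that may look less favourable. The change is best made before data are collected, because grade and relatedness are hard to reconstruct afterwards.

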6.1 Sample size

Logrank test is used to analyze the survival rates. The median recurrence time after liver transplantation for HCC which extends the Milan criteria is 12 months according to the literature. The median recurrence time is expected to increase to 24 months after treatment with lenvatinib. The experimental group and the control group were enrolled in the group according to the ratio of 1:1. The recruiting time is expected to be 12 months and the study time is expected to be 36 months. At least 47 cases were calculated for each group. Since it is assumed that 10% of the samples may be lost due to the adjustment of the intentional treatment population, 53 cases will be needed for each group eventually.

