6.2 Statistical Methods

The researcher is responsible for checking and preserving all the data, and handing over the data results to professional statisticians for analysis. Survival curves are estimated using the Kaplan – Meier method. For identification of independent prognostic factors, the Cox proportional hazard model was used in the univariate and multivariate analyses. All statistical analyses were performed using the SPSS (version 22.0). Statistical significance was defined as $p < 0.05$.

7. Emergency Event Management

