7.2 Emergency management

During this research period, [name] has professional skills and is responsible for medical emergencies and related treatment. If you encounter large-scale or critical events, please report to the head of the department head and hospital timely.

8. Data security and monitoring plan

None.

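### Does listing 1-, 3- and 5-year rates beside a log-rank test raise the type I error of the recurrence claim above 5%?

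*Combined protocol and SAP*

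**What the plan says.** Section 4.4 names one primary variable: "The primary endpoint is tumor recurrence which refers to the time from treatment to tumor recurrence". It then adds: "The 1, 3, 5-year recurrence-free survival rate and the 1, 3, 5-year overall survival rate will be analyzed". No test, hypothesis or order of importance is attached to those rates, and follow-up is given as 5 years.

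Section 6.1 opens with "Logrank test is used to analyze the survival rates" and goes straight on to one sample-size calculation: median time to recurrence 12 months in controls and 24 months on lenvatinib, 1:1 allocation, 47 per group, and 53 after a 10% allowance for loss. On timing it says "The recruiting time is expected to be 12 months and the study time is expected to be 36 months". Power and sidedness are not given.

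Section 6.2 names Kaplan-Meier curves, Cox models for prognostic factors, and one significance threshold of 0.05. It does not mention multiplicity.

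**The concern.** Three features together make this look like a multiplicity problem. The log-rank test is tied to survival rates in the plural. The only such rates listed are those at 1, 3 and 5 years. One unadjusted threshold covers everything. Taken literally, recurrence-free survival would be tested at three horizons, with nothing to say which one decides.

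The sized analysis also matches none of the three. At study month 36, after 12 months of recruitment, patients have 24 to 36 months of follow-up.

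The setting adds to the worry. The trial is open and single-centre, tumor markers and ultrasound are checked monthly, and section 8 contains no monitoring plan. If the horizon with the smallest p-value could be reported as the primary result, a false claim of benefit would become roughly two to three times as likely as the nominal 2.5%.

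**Working it through.** **Inputs.** Section 6.1 gives medians of 12 and 24 months, 1:1 allocation, 12 months' recruitment, 36 months' study time (read as the total), 47 per group and 10% loss. Section 2 gives 54 per group. Section 6.2 gives the 0.05 threshold. Assumed: two-sided test, 80% power, exponential times (hazard ratio 12/24 = 0.5), uniform recruitment.

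**1. Reproduce the plan's sample size as a single test.**

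- Events (Schoenfeld): 4 × (1.960 + 0.842)² / (ln 0.5)² = 65.3.
- Probability of recurrence by study month 36: 1 − [exp(−24λ) − exp(−36λ)] / (12λ), with λ = ln 2 / median. This gives 0.820 (control) and 0.577 (lenvatinib).
- Per group: 65.3 / (0.820 + 0.577) = 46.8, so 47. Rounding up to 66 events first gives 48.
- With loss: 47 / 0.9 = 52.2, so 53.
- Power with 47 per group: 65.7 events; √65.7 / 2 × 0.693 − 1.960 = 0.85, which is 80.2%. With 54 per group: 75.4 events and 85.3%.

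Other settings also give 47: Freedman's formula, one-sided, at 85% power; or Schoenfeld, two-sided, at 85% power with 36 months added after recruitment. Each of these is still one log-rank test at 0.05.

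**2. Type I error of that single test.** A null simulation of the whole-curve log-rank test (54 per group, null medians 12 to 60 months, 20,000 runs per scenario) gave 4.9-5.4%, in line with the nominal 5%.

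**3. Type I error if three horizons were tested and any one sufficed.** This success rule is not in the plan. The three statistics are treated as trivariate normal, each tested at two-sided 0.05.

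| Test at 12, 36, 60 months | Common median | Quantity setting the correlation | Correlations (12-36, 12-60, 36-60) | Any p < 0.05 | In favour of lenvatinib |
|---|---|---|---|---|---|
| Log-rank cut off at each time | 12 | event probability 0.500, 0.875, 0.969 | 0.756, 0.718, 0.950 | 9.3% | 4.6% |
| Log-rank cut off at each time | 24 | event probability 0.293, 0.646, 0.823 | 0.673, 0.596, 0.886 | 10.4% | 5.2% |
| Kaplan-Meier rates | 12 | (1−S)/S = 1, 7, 31 | 0.378, 0.180, 0.475 | 13.3% | 6.7% |
| Kaplan-Meier rates | 24 | (1−S)/S = 0.414, 1.828, 4.657 | 0.476, 0.298, 0.627 | 12.6% | 6.3% |

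Each correlation is the square root of the ratio of the smaller to the larger quantity. Simulation over null medians 12 to 60 months gave 9.2-11.3% for the cut-off log-rank tests. For Kaplan-Meier rates it gave 9.5-13.0% on the log-log scale and 13.0-14.6% for plain differences. Three independent tests would give 1 − 0.95³ = 14.3%.

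**4. Which reading does the text support?**

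- A standard log-rank test compares whole curves, not a rate at one time.
- The sentence naming it introduces a calculation with one pair of medians, and step 1 shows that calculation is one test.
- Section 4.4 names a single primary variable, the same one that was sized.
- Section 6.2 names Kaplan-Meier estimation, the usual way to report yearly rates. It names no comparison at a fixed time, so the figures near 13% rest on a test the plan never mentions.
- The yearly rates are of recurrence-free survival. The plan does not define that term or say how deaths count, so they need not be the same variable as time to recurrence.

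**The case for a change.** The strongest reply is that a named endpoint is not yet a named comparison. Even with one whole-curve test, the plan gives no analysis date or event count: section 6.1 works to 36 months and section 4.4 to 5 years. The choice affects power. With medians 12 and 24 months and 47 to 54 per group, power is 80-85% at study month 36 and 89-93% after 5 years of follow-up for each patient. Cut off at 1 year it would be 56-62%, and at 3 years 83-88%. In an open trial, an unwritten date could in principle be settled after results are seen.

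The omission is real: the date, the power, the sidedness and the descriptive status of the yearly rates are all unstated. It does not establish an inflated error rate. The plan schedules no repeated analyses; the quarterly entry, "liver MR or CT scanning every 3 months, lung CT every 3 months", is an imaging schedule. The 5-year follow-up is compatible with a sample size worked to month 36. Section 6.2 also sends the data to statisticians: "The researcher is responsible for checking and preserving all the data, and handing over the data results to professional statisticians for analysis". The empty section 8 concerns data security and monitoring and does not bear on which test is primary.

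**Conclusion.** The concern does not hold as a fault in the plan. On the design that was sized, there is one log-rank test of time to recurrence and its type I error is 5%. The 9-10% (cut-off log-rank) and roughly 13% (Kaplan-Meier rates) arise only if each recurrence-free rate were tested at 0.05 and any one sufficed, a rule found nowhere in the documents.

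What remains is missing detail that analysts fill sensibly: a two-sided test of the whole curve, with the yearly rates reported as Kaplan-Meier estimates. The analysis date is the sponsor's to record. A single test at either study month 36 or the end of follow-up keeps the 5% level and has at least 80% power under the plan's assumptions. Patient numbers, visits and method stay as they are.

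This rests on exponential times, uniform recruitment, a two-sided 0.05 level, and one analysis at a date not chosen from the results.

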6.2 Statistical Methods

The researcher is responsible for checking and preserving all the data, and handing over the data results to professional statisticians for analysis. Survival curves are estimated using the Kaplan – Meier method. For identification of independent prognostic factors, the Cox proportional hazard model was used in the univariate and multivariate analyses. All statistical analyses were performed using the SPSS (version 22.0). Statistical significance was defined as $p < 0.05$.

7. Emergency Event Management

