recurrence of hepatocellular carcinoma and the side effects of lenvatinib. The efficacy and safety of lenvatinib in patients of high-risk hepatocellular carcinoma are observed, and the clinicopathological factors affecting the efficacy of lenvatinib are analyzed.

When side effects of lenvatinib occur, the dosage can be reduced according to the patients' condition until discontinuation. When tumor recurrence occurs, a multidisciplinary team will draw up specific treatment plans according to the patients'

condition, including surgical resection, interventional therapy, radiofrequency therapy, radiotherapy and targeted therapy (Patients in the control group can add lenvatinib, and patients in the lenvatinib group can decide whether to continue using it according to the patients' condition).

3. Research population

3.1 This study is a single center clinical study. The cases are from patients with hepatocellular carcinoma who underwent liver transplantation in the liver surgery department of Shanghai Renji Hospital.

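### Section 2 promises an analysis of factors that affect lenvatinib's efficacy, but section 6.2 provides only prognostic-factor Cox models (minor; the primary comparison is unaffected)

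*Combined protocol and SAP*

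**What the plan says.** Section 1 sets the purpose: "The aim of this study is to observe the efficacy and safety of lenvatinib" in preventing recurrence after transplantation. Section 2 adds, in one clause, that "the clinicopathological factors affecting the efficacy of lenvatinib are analyzed".

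Section 6.2 describes Kaplan–Meier curves and one kind of factor analysis: "For identification of independent prognostic factors, the Cox proportional hazard model was used in the univariate and multivariate analyses". It closes with a general rule, "Statistical significance was defined as" p below 0.05. The comparison of the arms is named in section 6.1: "Logrank test is used to analyze the survival rates".

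No section supplied lists candidate factors, specifies a treatment-by-factor term or a subgroup contrast, or says whether the Cox models are fitted in one arm or both.

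**The concern.** Efficacy is a contrast between the arms. A factor that affects efficacy is therefore one across which the treatment hazard ratio changes. A Cox model with main effects only imposes the same treatment hazard ratio at every factor level, and a model without a treatment term does not estimate a treatment effect at all. Neither can show what section 2 promises.

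Two consequences follow if the plan is carried out as written. A factor that predicts recurrence equally in both arms could be reported as identifying who benefits from lenvatinib. And if the investigators do look for differences in effect, the factors and the method would be chosen after the data are seen.

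**Working it through.** **1. Text side by side.** Section 2 asks about factors that change the treatment effect. Section 6.2 models factors associated with outcome. These are different estimands: with treatment Z and factor X, the first is the coefficient c in log hazard = log baseline + aZ + bX + cZX, and the second is b. The plan specifies b and never mentions c.

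**2. The plan's own sample size.** Inputs from section 6.1: medians 12 and 24 months (hazard ratio 0.5 under exponential times), 1:1 allocation, "The recruiting time is expected to be 12 months and the study time is expected to be 36 months". Power and sidedness are not stated; 80% and two-sided 0.05 are assumed.
- Events (Schoenfeld): 4(1.960 + 0.842)² / (ln 2)² = 65.3, so 66.
- Event probability with uniform accrual over 12 months and a cut at 36 months: 1 − (e^(−24λ) − e^(−36λ)) / (12λ), giving 0.820 (control) and 0.577 (lenvatinib), mean 0.699.
- Per arm: 65.3 / (2 × 0.699) = 46.8, so 47. With 10% loss, 47 / 0.9 = 52.2, so 53.

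Both stated figures, 47 and 53, reproduce. They size the main comparison only.

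**3. What a treatment-by-factor analysis could deliver at 36 months.** Section 2 enrols 54 per arm. Expected events are 54 × 0.820 = 44.3 and 54 × 0.577 = 31.2, about 75 in all. Assume a binary factor with 50% prevalence.
- Simple formula: SE = √(4 / (75.4 × 0.5 × 0.5)) = 0.46. This treats events as evenly spread over the four treatment-by-factor cells, which they are not.
- Uneven cells, for a true ratio of 2 (lenvatinib hazard ratios 0.354 and 0.707 by factor): expected events are 22.1 and 22.1 (control), 12.3 and 19.0 (lenvatinib). SE = √(1/22.1 + 1/22.1 + 1/12.3 + 1/19.0) = √0.224 = 0.47.
- Simulation of the fitted Cox model under the same assumptions: median SE 0.48, power about 30%. This is the figure to use.
- CI factor: exp(1.96 × 0.482) = 2.6.
- Power check: ln 2 / 0.482 − 1.96 = −0.52, which corresponds to 30%.
- Ratio detectable with 80% power: exp(2.80 × 0.482) = 3.9.

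**4. At five years.** Section 4.4 states "The follow up duration time is 5 years". At 60 months per patient, a constant hazard gives 54 × (1 − 2^−5) = 52.3 and 54 × (1 − 2^−2.5) = 44.5, about 97 events. Simulated SE is about 0.42, and the CI factor is exp(1.96 × 0.42) = 2.3. This is optimistic: it has 52.3 / 54 = 97% of controls recurring, with no cured patients and no death before recurrence.

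**5. Optional adjusted analysis (separate from the mismatch).** Simulated power at 36 months, log-rank test versus Cox model adjusted for one binary baseline factor, with a treatment hazard ratio of 0.5 within factor levels:

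| Factor HR | Log-rank | Adjusted Cox | Change (points) |
|---|---|---|---|
| 1 | 0.854 | 0.848 | −0.6 |
| 1.5 | 0.833 | 0.840 | +0.7 |
| 2 | 0.799 | 0.835 | +3.6 |

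If the unadjusted hazard ratio is held near 0.5 instead, the change at a factor HR of 2 is similar (0.842 to 0.875, +3.3 points). The documents give no prognostic effects, so the factor HR is a range and not an estimate.

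**The case against.** The best reply is that section 2 is loosely worded and means factors associated with outcome, in which case section 6.2 is the intended match. The documents do not settle this, and that part of the reply stands: the point is a mismatch to be resolved, and rewording section 2 is as good a fix as adding an analysis. It is also fair that the item is a single clause. It is not in the stated aim, it is not an endpoint in section 4.4, and it plays no part in the sample size. That supports treating it as minor.

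The low precision is a further argument for rewording, since a treatment-by-factor analysis of about 75 events will seldom identify who benefits. It is no argument for leaving the mismatch, because a prognostic model does not answer the question at any sample size.

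Three stronger readings are tempting and not supported. A reader might infer that the efficacy conclusion is compromised; it is not, because the log-rank comparison uses none of these models. A reader might infer a specific inflated false-positive rate from applying p below 0.05 to many factors; the plan specifies no interaction tests and no number of factors, so no rate can be computed from it. A reader might infer that leaving out covariate adjustment is an error; an unadjusted log-rank test is valid in a randomised trial, and adjustment is an option only.

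**Conclusion.** The mismatch holds and is minor. The plan states an analysis of factors affecting efficacy and provides a method only for prognostic factors; either the method or the wording of section 2 must change. The finding itself rests on the text and needs no numerical assumption.

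The figures describe only how imprecise the added analysis would be: about 75 events, SE about 0.48, CI factor about 2.6 and about 30% power for a ratio of 2 at 36 months. They assume 54 per arm, exponential recurrence times with the medians of section 6.1, no loss to follow-up and a 50% binary factor. Loss or a less balanced factor would worsen them. The five-year figures (SE about 0.42, CI factor about 2.3) should be read as a favourable limit.

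**What to change.** Choose one of two.

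(i) In section 6.2, name up to three baseline factors before analysis. For each, fit a Cox model on all randomised patients with treatment, factor and treatment-by-factor terms. Report the ratio of hazard ratios with its 95% CI, label it exploratory (the documents do not label it at present), and make no claim of significance at p below 0.05. State that the prognostic models do not address efficacy. The cost is a few lines of text; SPSS, already named in the plan, fits the model. The downside is the imprecision shown above.

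(ii) Change the clause in section 2 to refer to prognostic factors, so that it matches section 6.2. The cost is a few words, and the question of who benefits is given up.

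A separate, optional improvement that corrects no error: keep the log-rank test as primary and prespecify one supportive treatment hazard ratio from a Cox model adjusted for one or two baseline factors. Alpha-fetoprotein and microvascular invasion on pathology are possible examples; the documents do not say that either is prognostic. Use values obtained before randomisation, in line with section 2 ("The baseline data of patients are collected before allocation"), because section 4.1 times the serological and imaging tests relative to treatment, which is not defined for controls. At 36 months the supportive analysis would change power by about −0.5 point if the factor is not prognostic and by about +4 points at a factor HR of 2. The adjusted hazard ratio is conditional on the chosen factors and can differ from the unadjusted one. Power of the primary test is unchanged.
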